4. To determine the influence of biological variables (e.g. mean corpuscular volume and hematocrit, age, weight, sex) on drug concentrations.
5. Compare drug concentrations in DBS from fingerstick versus transferring blood from blood tubes.

Primary outcomes:

Benchmark concentrations of TFV-DP in DBS and PBMCs, and the dosing frequency (i.e., doses per week) required to generate them.

The Women TDF-FTC Benchmark Study

Pharmacology of TDF-FTC Pre-exposure Prophylaxis in Kenyan Cisgender women

STUDY SUMMARY

PROTOCOL ABSTRACT/SUMMARY

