2.3 Primary Objectives

- 1) To define the cisgender women-specific expected blood concentrations and dose-proportionality for TFV-DP in DBS and PBMCs in cisgender women using directly observed TDF/FTC therapy at 2, 4, 7 doses per week.
- 2) To establish a model to predict adherence rate to TDF/FTC by level of TFV-DP in DBS for cisgender women.

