7.2 Study endpoints

Aim 1: Mean, variance, and dose proportionality for TFV-DP in plasma, DBS, and PBMC for 2, 4, 7 of DOT TDF-FTC dosing per week.

Aim 2: Prediction model of adherence rate by level of TFV-DP in DBS.

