mixed procedure will be utilized for model (Eqn 1), again assuming a random subject effect. For the primary analysis, we assume no effect of ‘non-daily dosing’ regimens; although this will be examined in a secondary analysis. If dose proportionality is not shown, we will examine proportionality separately for each of the “non-daily dosing” dosing regimens. If dose proportionality is still not demonstrated when adherence regimens are examined separately, we will consider dose as a categorical predictor. Change in objective function and/or AIC will be used to compare models. This approach will be used to further probe dose proportionality and the final model(s) will be used as a basis for simulation studies. Additionally, we will fit a model with following first-order kinetic equation to the TFV-DP data: $C_t = C_{ss} * (1 - e^{-k*t})$, where C_t is the TFV-DP at time t (i.e., day 4, weeks 1, 2, 3, 4, 5, 6, 7, 8), C_{ss} is the fitted concentration at the steady-state plateau and k is the fitted elimination rate constant, and half-life is $\ln(2)/k$. The fitted C_{ss} will be used in the dose-proportionality model. These approaches use non-compartmental and a simple one-compartment model, respectively. Finally, the percentage of dose can be used as a regressor because the concentration at steady-state is directly proportional to dose frequency and TFV-DP clearance [$C_{ss} = (\text{dose rate})/CL$]. Time post dose does not have to be accounted for because it does not impact the TFV-DP concentration given the 17-day half-life. Importantly, we have used these approaches to assess dose proportionality in two similarly designed studies that have been published. [<https://pubmed.ncbi.nlm.nih.gov/32539288/>].⁷⁴⁻⁷⁸

Primary outcome 2: The goal is to identify TFV-DP cut points associated with adherence levels. For the primary analyses, we will attempt to discriminate adherence for 2, 4 and 7 dosing based upon TFV-DP. As above, we will combine the “non-daily dosing” regimens. Linear mixed models with random intercepts, 25th percentiles, and receiver operating characteristics curves will be used to generate predicted concentration thresholds for varying dosing frequency (ranging from 2 to 7 doses/week) for each matrix-analyte pair. Analyses will be adjusted for age, contraception use, study arm, BMI, eGFR, and hematocrit.

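### Primary objective 2 promises a model predicting adherence from DBS TFV-DP level, but the primary analysis stops at cut points: a coarse band, no doses-per-week estimate or prediction interval, and no view of misclassification at 3, 5 or 6 doses

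*Combined protocol and SAP*

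**What the plan says.** Section 2.3 gives primary objective 2 as "To establish a model to predict adherence rate to TDF/FTC by level of TFV-DP in DBS for cisgender women". Section 7.2 gives the matching endpoint as "Prediction model of adherence rate by level of TFV-DP in DBS". Both start from a level and end at adherence.

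Section 7.3.1, primary outcome 2, states the aim differently: "The goal is to identify TFV-DP cut points associated with adherence levels". It continues that "we will attempt to discriminate adherence for 2, 4 and 7 dosing based upon TFV-DP", and then names the tools and their output: "Linear mixed models with random intercepts, 25th percentiles, and receiver operating characteristics curves will be used to generate predicted concentration thresholds". Those thresholds are to be indexed by dosing frequency between 2 and 7 per week, separately for every combination of matrix and analyte. The covariates listed for these analyses include study arm.

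The Protocol Schema words the primary outcome closer to section 7.3.1: "Benchmark concentrations of TFV-DP in DBS and PBMCs, and the dosing frequency (i.e., doses per week) required to generate them".

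The only model with adherence as its outcome is the proportional-odds model in section 7.3.2, item 1. It is secondary, aimed at non-daily dosing patterns, and covered by the statement that secondary analyses generate hypotheses.

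**The concern.** In use, the level is known and the dosing is not. That is so for trial and programme samples, and for the archived Partners PrEP samples to which the Protocol Schema says the results will be applied. The reader of a DBS result needs to know which dosing frequencies are compatible with it. A threshold derived from women on known regimens gives a band, without saying how wide a range of doses per week fits the level.

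Two details add to this. First, the trial has arms only at 2, 4 and 7 doses/week, so observed sensitivity and specificity exist only at those frequencies. The overlap that matters most for a 7-dose cut is with 5 and 6 doses, where no woman is observed. Second, study arm is the dosing frequency. A model adjusted for arm cannot be applied to a woman whose dosing is unknown, and the adjustment competes with the dose effect that the thresholds are meant to express.

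At stake is whether the second primary objective is met as written, and whether users take a level above the top cut as evidence of daily dosing.

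**Working it through.** **The plan's own figure.** No precision or error figure is given for primary objective 2; section 7.4 sizes the trial on the precision of a mean. Its variability input reproduces: 405/1605 = 25.2%.

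**Inputs.** CV 25.2% (section 7.4, US men on daily dosing). Cuts at the 25th percentile (section 7.3.1), read as bands as in the threshold table of section 1.2.1. Arms at 2, 4 and 7 doses/week with 18 women each (section 7.5). Assumed: power-model slope of 1, log-normal levels, the same CV in every regimen. CVs of 35% and 45% are assumed to show the range.

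**Share above the 7-dose cut.**
- Log-scale SD: s = sqrt(ln(1 + 0.252²)) = 0.248.
- 7-dose cut in dose equivalents: 7 × exp(−0.6745 × 0.248) = 5.92. The level typical of 6 doses/week already lies above it.
- P(above cut | d doses) = P(Z > (ln 5.92 − ln d)/s). For d = 4: P(Z > 1.58) = 0.057. For d = 5: P(Z > 0.68) = 0.248. For d = 6: P(Z > −0.05) = 0.521.

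| Doses/week | CV 25.2% | CV 35% (assumed) | CV 45% (assumed) |
|---|---|---|---|
| 4 | 6% | 17% | 27% |
| 5 | 25% | 38% | 46% |
| 6 | 52% | 59% | 62% |
| 7 | 75% | 75% | 75% |

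The 75% is by construction. In the lower bands, at CV 25.2%, 31% of 3-dose women fall between the 4-dose and 7-dose cuts.

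**What the ROC step would show.** On the three arms, this cut has 75% sensitivity for daily dosing, and about 6% of the 4-dose arm lies above it. The 25% and 52% for 5 and 6 doses cannot appear, because nobody takes those doses.

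**Inverse prediction for one level.** With x = ln(dose), N = 54 and slope 1, the 90% interval is the set of x₀ with |ln y − μ − x₀| ≤ t × s × sqrt(1 + 1/N + (x₀ − x̄)²/Sxx).
- x̄ = (ln 2 + ln 4 + ln 7)/3 = 1.342.
- Sxx = 18 × (0.649² + 0.044² + 0.604²) = 14.2.
- t(0.95, 52 df) = 1.675.

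For a level typical of 4 doses/week, the half-width on the log scale is about 1.675 × 0.248 × 1.015 = 0.42. The interval is 2.6 to 6.1 doses/week. At 15 women per arm it is the same to one decimal.

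| Level typical of | CV 25.2% | CV 35% (assumed) | CV 45% (assumed) |
|---|---|---|---|
| 2 doses/week | 1.3 to 3.0 | 1.1 to 3.6 | 0.9 to 4.1 |
| 4 doses/week | 2.6 to 6.1 | 2.2 to 7 | 1.9 to 7 |
| 7 doses/week | 4.6 to 7 | 3.9 to 7 | 3.4 to 7 |

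Upper limits above 7 are cut to 7, the daily maximum.

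**The case against.** The best defence is that the plan does go from level to adherence. Section 7.3.1 sets out to separate 2, 4 and 7 doses using TFV-DP, with ROC curves, and these bring sensitivity and specificity. The table in section 1.2.2 shows that the investigators already report thresholds with sensitivities and 95% confidence intervals. The Protocol Schema's primary outcome fits cut points, and the half-empty table in section 1.2.1 shows the intended product: level bands mapped to doses per week. Thresholds are planned across 2 to 7 doses, the final models are to support simulation, and section 7.3.2 adds an ordinal model that could return category probabilities.

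Much of this stands. A reader might infer that the primary analysis says nothing about adherence for a measured level, or gives no measure of error at all. The documents do not support that: it yields a band with ROC performance. Nor are the cut points wrong.

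What remains is narrower. A band is not the promised prediction model, and no interval is planned for a single level. Interpolated thresholds at 3, 5 or 6 doses come with no planned statement of how many women at other frequencies exceed them. The ordinal model and the ratio simulations are secondary and directed at non-daily patterns.

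It is also fair that the percentages above describe overlapping distributions. Inverse prediction would report that overlap and would not reduce it.

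**Conclusion.** The concern holds in this form: sections 2.3 and 7.2 promise a prediction model for adherence, while primary outcome 2 in section 7.3.1 delivers cut points and a coarse band, with no doses-per-week estimate or prediction interval. ROC curves from three arms cannot show error at the untested frequencies.

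Under the stated assumptions, a quarter of 5-dose women and about half of 6-dose women would pass the 7-dose cut, and more if variability in Kenyan women exceeds that in US men. A level typical of 4 doses/week is compatible with roughly 2.6 to 6.1. These figures rest on slope 1, log-normality and a borrowed CV. They illustrate the size of the gap and do not predict the trial's results.

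A reader might take 52% as the chance that a woman above the cut is taking 6 doses. It is not: it is the chance of exceeding the cut given 6 doses. The reverse probability also depends on how dosing is distributed in the population tested, which the documents do not give.

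The change should be made. It affects how a primary objective is reported; sample size and conduct are untouched.

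**What to change.** In section 7.3.1, primary outcome 2:

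1. Keep the cut points and add inverse prediction from Eqn. 1. For level y, predicted doses/week = exp[(ln y − μ)/β], truncated at 7, with a 90% prediction interval, reported over the observed DBS range. Use total (between- plus within-woman) variance; with one week 8 value per woman, only that sum can be estimated.
2. Name the fallback. A slope other than 1 does not break the formula, but the plan's switch to categorical dose does. In that case fit an ordinal model on DBS TFV-DP and report category probabilities.
3. For each cut point, report the model-based share of women on 2, 3, 4, 5, 6 and 7 doses/week who exceed it, labelled as P(above cut | dose) and not P(dose | level).
4. Remove study arm from the covariates of the prediction and threshold models.

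The cost is a few lines of SAP text and one or two tables, from a model already being fitted. The fallback adds one ordinal fit. No new data or participants are needed.

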2.5.1 Study design for non-pregnant cisgender women

This is an open-label, randomized, three-arm, directly observed therapy, pharmacologic study. HIV-uninfected non-pregnant cisgender women at low risk for HIV will be randomly assigned to 1 of 3 dosing frequencies of DOT TDF/FTC PrEP (**Figure 4**): 2, 4, or 7 doses per week to help differentiate poor and modest from perfect dosing (**Figure 4**).

Figure 4: Schema for directly observed TDF/FTC PrEP dosing and pharmacologic sampling

Enrollment will continue until 54 for non-pregnant evaluable participants (i.e., participant with completed data on dosing and PK samples) are enrolled.

- **Group #1:** “7 doses per week or Perfect Adherence arm”— cisgender women will receive a single tablet of co-formulated 300 mg TDF/ 200mg FTC once daily (7 doses per week).
- **Group #2:** “4 doses per week or Moderate Adherence arm” — cisgender women will receive a single tablet of co-formulated 300 mg TDF/ 200mg FTC tablet on Monday, Tuesday, Thursday, Friday.
- **Group #3:** “2 doses per week or Poor Adherence arm” — cisgender women will receive a single tablet of co-formulated 300 mg TDF/ 200mg FTC tablet on Monday and Tuesday.

Justification for non-daily dosing of PrEP groups:

In this study we propose to randomize cisgender women (non-pregnant cohort) to non-daily dosing of PrEP (2, or 4 doses per week). The non-daily dosing is needed to help investigate and demonstrate dose proportionality of TFV and TFV-DP concentrations. The adherence-concentration thresholds derived from this dosing frequency will help guide clinical decisions on drug levels associated with HIV protection in cisgender women and adherence level required to achieve those concentrations. Only daily PrEP is recommended by WHO and the Kenya national guidelines for protection from vaginal HIV exposure and we have carefully considered the risks associated with non-daily in planning this proposal. As detailed in eligibility section, only non-pregnant cisgender women at low HIV risk based on Kenya guidelines will be enrolled and cisgender women will receive full package of HIV prevention, including risk reduction counseling, condoms and STI treatment at each visit. We will also perform monthly HIV testing.

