7.5 Randomization and Blinding Procedures

The study design for non-pregnant cohort will be an open-label, randomized study with three arms. The randomization assignments cohort will be made at enrollment if the participant is eligible and agrees to enroll. Randomization will be according to the PrEP dosing frequency and vaginal tissue collection plan (either sampling day 4 or day 7) 1:1:1 fashion programmed by the study statistician and generated from REDcap. Randomization will be done at enrollment.

The allocation of participants for the 3 study arms will be the following:

	2 doses per week	4 doses per week	7 doses per week	Total
Total	18	18	18	54

The study design for the pregnant cohort will be an open-label, non-randomized study with only DOT PrEP daily dosing regimen (7 doses per week).

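### Primary outcome 2 adjusts its threshold analysis for study arm, which is the dosing frequency being predicted, so the adjusted model fails as written; the sentence combining the non-daily regimens also needs defining

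*Combined protocol and SAP*

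**What the plan says.** Section 7.3.1, primary outcome 2, sets a three-level aim: "we will attempt to discriminate adherence for 2, 4 and 7 dosing based upon TFV-DP". The next sentence reads "As above, we will combine the “non-daily dosing” regimens". The tools follow: "Linear mixed models with random intercepts, 25th percentiles, and receiver operating characteristics curves will be used to generate predicted concentration thresholds", covering frequencies from 2 to 7 doses per week for each matrix-analyte pair. The paragraph ends: "Analyses will be adjusted for age, contraception use, study arm, BMI, eGFR, and hematocrit".

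Two other sections fix the meaning of these terms. Section 7.5 introduces its allocation table with "The allocation of participants for the 3 study arms will be the following", and the columns are 2, 4 and 7 doses per week with 18 women each. Section 2.5.1 describes the same mapping and identifies the non-daily regimens: "non-daily dosing of PrEP (2, or 4 doses per week".

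The back-reference in the combining sentence appears to point to primary outcome 1, which states "For the primary analysis, we assume no effect of ‘non-daily dosing’ regimens". In that analysis dose stays in the power model as log(D), at levels 2, 4 and 7.

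**The concern.** A covariate adjustment should remove variation that is not of interest. Here the list includes the quantity the analysis is meant to recover. Once arm is held fixed, dosing frequency does not vary, so nothing is left for TFV-DP to predict. People who will later use the thresholds, on archived trial samples or in PrEP programmes, also have no arm to adjust for.

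The combining sentence raises a second question. Each non-daily regimen is a single arm, so merging them would erase the 2 versus 4 distinction named one sentence earlier.

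Primary objective 2, the model that predicts adherence from TFV-DP in DBS, is at stake. If the written model cannot be fitted, the analyst must choose another after the data are in hand.

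**Working it through.** The plan gives no equation or numerical result for primary outcome 2, so there is no figure to reproduce. The checks below are structural, with illustrative sizes.

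**1. Dose term plus arm in a linear model.** Inputs: 18 women per arm (7.5), one dosing frequency per arm (2.5.1, 7.5). The columns are intercept, ln(dose), an indicator I4 for the 4-dose arm and an indicator I7 for the 7-dose arm. Since ln 2 = 0.693, ln 4 = 1.386 and ln 7 = 1.946,

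ln(dose) = 0.693 + 0.693 × I4 + 1.253 × I7, exactly.

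The matrix has 4 columns and rank 3. Adding five further covariates gives 9 columns and rank 8. The residual sum of squares of ln(dose) given arm is zero, so the dose slope is not estimable. A random intercept does not help, because dose and arm are both constant within a woman.

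**2. ROC with TFV-DP adjusted for arm.** Inputs: CV 25.2% (7.4, from daily dosing in US men). Assumptions: lognormal concentrations, the same CV in each arm, and means proportional to dose.

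- Log SD: s = √ln(1 + 0.252²) = 0.248.
- AUC = Φ[ln(dose ratio) / (s√2)], with s√2 = 0.351.
- 2 v 4: Φ(0.693 / 0.351) = Φ(1.975) = 0.976.
- 4 v 7: Φ(0.560 / 0.351) = Φ(1.595) = 0.945.
- After arm means are removed from log TFV-DP, the groups have the same distribution and both AUCs are 0.50.

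For an assumed CV of 20% to 50%, the unadjusted AUC runs from 0.99 to 0.85 (2 v 4) and from 0.98 to 0.80 (4 v 7). The arm-adjusted value stays at 0.50 throughout.

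**3. What survives.** Take the week-8 daily mean of 1445 fmol/punch (7.4) and the assumptions of step 2. The means are then 413, 826 and 1445, and the 25th percentiles by arm are about 339, 677 and 1185. These need no covariate model. A simulated model with arm as the exposure, no second dose term and five covariates recovers nearly the same values: about 340, 678 and 1190.

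**4. Literal pooling of the 2- and 4-dose arms.** Inputs: MSM 25th percentiles of 350 and 700 (1.2.1) and s = 0.248.

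- Medians: 350 / exp(−0.6745 × 0.248) = 350 / 0.846 = 414, and 700 / 0.846 = 827.
- The pooled 25th percentile x solves ½Φ[ln(x/414)/s] + ½Φ[ln(x/827)/s] = 0.25. At x = 413 the two Φ terms are about 0.497 and 0.003, which satisfies it.
- 413 / 350 = 1.18, so it lies 18% above the 2-dose value. 413 / 700 = 0.59, so it lies 41% below the 4-dose value.

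No 2 v 4 cut point exists under this reading.

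**The case against.** The strongest defence is that the text never states that a dose term and arm enter the same model. Concentration is the response in the mixed model, so study arm could be the dose term, adjusted for the other variables. Section 7.3.2 repeats much of the same list as key study variables, which suggests a reused list. This softens the point but does not remove it. The sentence places arm among the adjustment variables and nowhere calls it the exposure. A model with arm as a three-level factor gives values only at 2, 4 and 7, whereas thresholds are promised across the range from 2 to 7.

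Three stronger readings are tempting, and the documents do not support them.

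- *The 2/4/7 cut points cannot be obtained.* Section 7.3.1 also lists 25th percentiles, which can be taken by arm without adjustment. Section 7.3.2 plans a saturated model with a separate mean for each dose group. The MSM benchmarks are themselves 25th percentiles by dosing frequency.
- *The plan merges the 2- and 4-dose arms, and its ROC would be trivially perfect.* The back-reference to primary outcome 1 also supports one common dose slope with no extra effect of dosing pattern, and the sentences on either side of the combining sentence need 2 and 4 to stay distinct. The perfect ROC requires arm as a classifier input, whereas the text bases discrimination on TFV-DP.
- *The threshold model wrongly omits time on drug.* No list of fixed effects is given for primary outcome 2, so this is inferred from silence. Primary outcome 1 uses week-8 and fitted Css values.

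**Conclusion.** The concern holds for the adjusted primary threshold model. Arm determines dosing frequency, so adjusting for it makes the dose effect inestimable (rank 3 of 4 columns) or, in an arm-adjusted ROC, reduces discrimination to chance. The rank result needs only the allocation table and a dose term in the model. The AUCs before adjustment rest on the assumed dose proportionality, lognormal distribution and common CV; the fall to 0.50 requires the log concentrations to differ between arms only in their means.

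Two variations do not rescue the wording. If doses actually observed replaced assigned doses, the collinearity would be near-complete instead of exact. If the pregnant cohort counted as a fourth arm, arm would still determine dose.

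The combining sentence is ambiguous on a primary outcome. It contradicts the three-level aim only if it means merging arms, and the 413 fmol/punch figure applies only then. The sample set for the thresholds is unstated, which calls for clarification and is not a demonstrated error.

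**What to change.** Make three changes to the primary outcome 2 paragraph of section 7.3.1, before concentration data are analysed:

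1. Delete study arm from the covariate list, leaving age, contraception use, BMI, eGFR and hematocrit. State that dosing frequency is the exposure in the mixed model and the outcome in the ROC analysis, and is never a covariate.
2. Replace the combining sentence with a statement that 2, 4 and 7 doses per week are kept as separate classes, and that the dose model uses a common dose slope with no extra effect of dosing pattern.
3. State that the thresholds use observed week-8 or fitted Css values, as in primary outcome 1.

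It would also help to say that the 25th percentiles are reported by arm without adjustment, since later users will apply them without covariates.

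The cost is a wording change to the analysis plan. Enrolment, dosing, sampling and sample size are unaffected.

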7.3.2 Secondary outcomes

1. Examine models to predict non-daily adherence based on TFV/FTC and TFV-DP in DBS.

We assume the modeling approaches of Aim-1. We will first consider a saturated model allowing a separate mean for each dose/adherence group. The results will then be compared to a reduced model with a class variable indicating non-daily dosing groups” or 100% dosing (that is, the effect of “non-daily dosing” adherence does not differ by dose groups). Drug concentration predictors of “non-daily dosing” will focus on TFV-DP in relationship to other drug moieties such as FTC-TP and FTC and TFV. For instance, the ratio of TFV-DP to FTC-TP may be used as a predictor of “2” versus “4 dosing per week. A proportional odds logistic approach which allows for an ordinal outcome and extensions which control for correlations between repeated measurements on a subject will be utilized in SAS or R statistical software. In addition, we will employ PK models (see Aim-1) to simulate TFV-DP to FTC-TP ratios for other dose regimens and estimate cut points for predicting non-daily dosing patterns.

2. To quantify the effect of pregnancy on the benchmark concentrations of TFV, TFV-DP, FTC, and FTC-TP in pregnant cisgender women using daily DOT FTC-TDF PrEP.

Using modeling approaches, we will compare the benchmark concentrations of TFV, FTC, TFV-DP, and FTC-TP between pregnant cisgender women using daily DOT FTC-TDF PrEP. Analyses will be stratified by age and pregnancy gestation.

3. Examine relationships among drug concentrations in plasma, RBC, DBS, and PBMC.

We will use mixed and non-linear mixed effects models to determine if concentrations in various matrices are related.

4. Evaluate the influence of demographics, biological) on drug concentrations.

Kruskal-Wallis parametric test will be used to compare demographics and key study variables (e.g., age, pregnancy, mean corpuscular volume and HCT, contraception use, study arm, BMI, eGFR). Secondary analyses are considered hypothesis generating and will not correct for multiple comparisons.

5. Compare drug concentrations in DBS from fingerstick versus transferring blood from blood tubes.

Since these are paired DBS samples, we will compute the ratio of TFV-DP in the two samples and a mixed model on the natural log of the ratio will be utilized to determine if CI is within 0.8 and 1.25, indicating equivalence. Bland-Altman analyses will also be evaluated.

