9 LABORATORY SPECIMENS AND BIOHAZARD CONTAINMENT

9.1 Laboratory evaluations and specimen collections

The following safety and monitoring laboratories will be collected at regular intervals during the study as described above: complete hematology panels, pregnancy tests (urine), and HIV (rapid or regular), serum creatinine, (estimated creatinine clearance), and HBV surface Ag test. The HIV and HBV tests will be used to screen HIV-negative volunteers for inclusion in the study. The tests are provided according to established laboratory procedures at site. These clinical laboratories/sites conform to CAP and/or CLIA-regulations, and the results will be posted to the medical record as positive or negative.

All pharmacological samples will be collected, processed, and stored according to standard operating procedures developed by the Colorado Antiviral Pharmacology Laboratory. On each pharmacological sample visit day, samples will be collected without regard to the dosing time within each day (i.e., sampling at convenience times rather than troughs). The only exception will be at the entry visit to be obtained at pre-dose. We will take a comprehensive approach to establish benchmark adherence-concentration thresholds for cisgender women and pregnant cisgender women using daily DOT TDF/FTC

PrEP by collecting samples for pharmacological measurements in multiple biologic matrices: plasma, whole blood, DBS, PBMCs, and vaginal tissue (non-pregnant cisgender women only) and archiving urine and hair samples. All cisgender women (non-pregnant and pregnant) will contribute to this comprehensive assessment during the up to 16 weeks of follow up (8 weeks of DOT PrEP and up to 8 weeks post DOT PrEP for post drug kinetics). Within each group, we will collect pharmacologic samples (plasma, whole blood, DBS, PBMCs) to measure the respective concentrations of TDF/FTC moieties at day 4 and weekly up to 8 weeks with daily DOT PrEP dosing and at week 9 and weeks 10-16 post DOT PrEP period, and in nonpregnant cisgender women, vaginal tissue at day 4, week 1, 2, 4, and 8.

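### Cut points on the TFV-DP:FTC-TP ratio carry mainly recency of dosing; entering both concentrations separately is a safer predictor of 2 versus 4 doses per week at almost no cost

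*Combined protocol and SAP*

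**What the plan says.** Item 1 of section 7.3.2 looks for predictors of non-daily dosing. It "will focus on TFV-DP in relationship to other drug moieties such as FTC-TP and FTC and TFV", and gives as an example that "the ratio of TFV-DP to FTC-TP may be used as a predictor of" 2 versus 4 doses per week, in a proportional odds model. That example is optional. The next step is not worded as an option: the team will use PK models to "simulate TFV-DP to FTC-TP ratios for other dose regimens and estimate cut points for predicting non-daily dosing patterns".

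Three other places bear on this.

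- **Section 7.3.1, primary outcome 1**, reasons that "the concentration at steady-state is directly proportional to dose frequency and TFV-DP clearance". It also says time after the dose can be left out, and gives the 17-day half-life of TFV-DP as the only reason.
- **Section 9.1** describes "sampling at convenience times rather than troughs". Section 5.2.2 allows a sampling window of up to three days.
- **Section 7.3.1, primary outcome 2**, sets the main cut points on TFV-DP itself: "we will attempt to discriminate adherence for 2, 4 and 7 dosing based upon TFV-DP".

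Section 7.3.2 also states: "Secondary analyses are considered hypothesis generating and will not correct for multiple comparisons".

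**The concern.** A ratio is a log-linear score with its weights fixed in advance at +1 for ln(TFV-DP) and -1 for ln(FTC-TP). If both analytes rise in proportion to the number of doses per week, the subtraction removes the common dose effect. What is left is the difference in how fast the two decay, that is, recency of dosing. Recency may separate the arms well or hardly at all, depending on the day of the week on which blood is drawn. The plan's argument for ignoring time after the dose covers the slow analyte only, and item 1 adds no timing term for FTC-TP.

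At stake is the usefulness of the simulated ratio cut points. The study means its thresholds to be applied in PrEP trials and programs, where the sampling day relative to dosing is not controlled.

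**Working it through.** **Inputs from the documents.** TFV-DP half-life 17 days (section 5.2.1). Dosing on Monday and Tuesday, or on Monday, Tuesday, Thursday and Friday (5.2.1). Week 8 visit at dose 56, window up to three days (5.2.2). TFV-DP CV 25.2%, from US men on daily dosing (7.4).

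**Assumptions.** First-order decay with equal doses, for both analytes. FTC-TP half-life 0.5-7 days. FTC-TP CV 25.2% with correlation 0 or 0.5, or CV 50% with correlation 0. Log-normal variation. First dose on a Monday, so day 56 is a Sunday.

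**Step 1: the plan's own figure.** 1 - 2^(-56/17) = 0.898, and 3.3 x 17 = 56.1 days. The stated value of about 90% of steady state at week 8 reproduces.

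**Step 2: week-average ratio.** Summing the decaying doses over 8 weeks and averaging over week 8, the 4-dose arm divided by the 2-dose arm gives 0.99-1.00 for the ratio at every FTC-TP half-life tried. Dose cancels on average.

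**Step 3: ratio on a single day of week 8, 4-dose arm divided by 2-dose arm.**

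| FTC-TP half-life (assumed) | Mon-Wed | Thu | Fri-Sun |
|---|---|---|---|
| 1 day | 1.65-1.71 | 0.53 | 0.24 |
| 2 days | 1.27-1.45 | 0.85 | 0.56 |
| 3 days | 1.14-1.30 | 0.94 | 0.71 |
| 7 days | 1.02-1.09 | 0.99 | 0.91 |

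The contrast changes direction within the week. One cut point that ignores the day therefore averages over opposing effects.

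**Step 4: AUC on a fixed day.** AUC = Φ(|ln fold| / (√2 × SD)).

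- TFV-DP: SD = √ln(1 + 0.252²) = 0.248, so √2 × SD = 0.351. The 4 v 2 fold is 1.82-2.13 across the week. Φ(0.599/0.351) = 0.96 and Φ(0.756/0.351) = 0.98.
- Ratio on Sunday, CV 25.2% and correlation 0.5: SD = 0.248 × √(2 × 0.5) = 0.248. A half-life of 2 days gives Φ(0.580/0.351) = 0.95; 7 days gives Φ(0.094/0.351) = 0.61.
- Ratio on Sunday, FTC-TP CV 50% and correlation 0: SD = √(0.248² + 0.472²) = 0.533. A half-life of 2 days gives Φ(0.580/0.754) = 0.78; 7 days gives 0.55.

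**Step 5: AUC by sampling window, simulated.** FTC-TP half-life 1-7 days; CV 25.2% with correlation 0.5, or CV 50% with correlation 0.

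| Sampling | Ratio | TFV-DP alone | Both jointly |
|---|---|---|---|
| Sunday, day 56 | 0.55-1.00 | 0.98-0.99 | 0.99-1.00 |
| Thursday-Sunday | 0.54-0.89 | 0.98 | 0.99 |
| Day 56 ±3, dosing stopped | 0.55-0.76 | 0.98 | 0.98-0.99 |
| Monday-Friday | 0.51-0.54 | 0.97 | 0.97-0.98 |

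Over half-lives of 0.5-7 days, sampling spread across week 8, or day 56 ±3 with dosing continuing, gives 0.50-0.66 for the ratio, 0.97 for TFV-DP and 0.97-0.99 jointly. In no scenario did the joint model fall below the ratio. That follows from nesting: the ratio is the joint score with weights +1 and -1.

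These are large-sample values. Estimates from 18 women per arm will be noisier.

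**The case against.** The strongest defence is that recency is itself a signal. On a Sunday the 2-dose arm is five days past its last dose and the 4-dose arm two days. If FTC-TP clears in about a day, the ratio can separate the arms almost perfectly and can beat TFV-DP alone. The plan also partly anchors the day: section 5.2 schedules enrolments on specific days, the week 8 visit is tied to dose 56, and the convenience sampling in section 9.1 refers to the time within a day. The stated aim is to "estimate cut points for predicting non-daily dosing patterns", for which recency is relevant.

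This stands against a stronger reading. A reader might infer that the ratio discards the dose signal and so would barely separate the arms. The documents do not support that. They give no half-life, variability or dose response for FTC-TP, and a single sample is not a weekly average. Nor do they support inferring that the study's main thresholds are compromised, since primary outcome 2 rests on TFV-DP. The ratio is offered as an example, and the wording does not exclude separate terms.

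The defence does not rescue the ratio as the scale for cut points. Its good performance needs a short FTC-TP half-life and a well-controlled late-week visit. Section 5.2.3.1 plans no timing relationship between blood draws and dosing, the window is up to three days, and section 5.2.1 lets the dosing days be adjusted before the study starts. Even in the case most favourable to the ratio, the joint model does at least as well.

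**Conclusion.** The point holds as a modest improvement of method. Under dose-proportionality of both analytes, the ratio is mainly a recency marker, and its value for telling 2 from 4 doses per week runs from almost none to almost perfect, depending on an FTC-TP half-life outside the documents and on the sampling day. Two separate log concentrations are robust across that whole range. The gain over TFV-DP alone is small (0.97 to 0.97-0.99 with spread sampling). The gain over the ratio is large in most scenarios and nil in the most favourable one.

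The sizes rest on the kinetic and variability assumptions listed above and on a CV from US men on daily dosing. The nesting argument does not depend on them. The analysis is secondary and exploratory, so the importance is low.

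**What to change.** In section 7.3.2, item 1:

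- Enter ln(TFV-DP) and ln(FTC-TP) as separate predictors in the proportional odds model.
- Derive the simulated cut points from the joint predicted probability, over the allowed range of sampling days.
- Keep the ratio as a descriptive summary.
- State that the reason for ignoring time after the dose applies to TFV-DP only. Handle timing for FTC-TP through sampling day, or through a sensitivity analysis by sampling day.
- Do not enter time since last dose as a predictor of arm. The schedule largely fixes it (five days v two on a Sunday), so it would leak the outcome into the model.

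The cost is a change of wording and one extra coefficient, with no new samples or assays. The downside is that a two-variable rule is slightly less simple to report than a single ratio.
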